1. VERSION HISTORY

Table 1. Summary of Changes

Version/ Date	Associated Protocol Amendment	Rationale	Specific Changes
1 / 18 Oct 2023	Original 08 Aug 2023	N/A	N/A

2. INTRODUCTION

PF-07220060 is a selective cyclin-dependent kinase (CDK)4 inhibitor that is currently being investigated in participants with metastatic or advanced solid tumors. PF-07220060 differs from currently approved dual CDK4/6 inhibitors in that it displays greater CDK4-over-CDK6 selectivity and is therefore hypothesized to drive tumor growth inhibition through greater CDK4 selectivity, while minimizing CDK6 driven hematopoietic effects. This may translate to improved efficacy and tolerability over other CDK4/6 inhibitors.

The purpose of the study will be to investigate the metabolism and excretion following a single oral administration of [¹⁴C]PF-07220060 under fasted condition in healthy male participants. The data generated from this study will be used to assess clearance mechanisms for PF-07220060 as well as identify metabolites that should be qualified to adhere to the International Council for Harmonisation of Technical Requirements for Pharmaceuticals for Human Use (ICH) (M3) R2 guidance. In addition, this study will characterize the fraction of dose absorbed and bioavailability of orally administered PF-07220060 under the fasted condition, in reference to an intravenous (IV) infusion of [¹⁴C]PF-07220060 (given as a microtracer microdose infusion following administration of an oral unlabeled dose), and will also assess pharmacokinetic (PK) parameters of PF-07220060 following both oral and IV administration of [¹⁴C]PF-07220060.

This study will also evaluate sensory and taste attributes (eg, bitterness and tongue/mouth sensation) of the PF-07220060 oral suspension to guide the future development of pediatric friendly oral formulations.

This SAP provides the detailed methodology for summary and statistical analyses of the data collected in Study C4391010.

2.1. Modifications to the Analysis Plan Described in the Protocol

None.

2.2. Study Objectives, Endpoints, and Estimands

The following are the objectives and endpoints in this study. Estimand framework will not be applied to this Phase 1 study in healthy participants.

Objectives	Endpoints
Primary:	Primary:

 To characterize the rate and extent of excretion of total radioactivity following administration of a single oral dose of [¹⁴C]PF-07220060. 	
 Mass Balance: Cumulative recovery (%) of radioactivity in urine and feces (adjusted for vomitus, if any), expressed as a percent of total oral radioactive dose administered (quantification by AMS).

 To characterize the metabolic profile for PF-07220060 and identify the circulating and excreted metabolites of PF-07220060 following administration of a single oral dose of [¹⁴C]PF-07220060. 	
 Metabolic profiling/metabolite identification and determination of relative abundance of [¹⁴C]PF-07220060 and its metabolites in plasma, urine and feces, if possible (Cohort 1).
Secondary:	Secondary:

 To determine the absolute oral bioavailability (F) of PF-07220060 from a single oral dose of PF-07220060 under fasted conditions followed by a single IV microdose of [¹⁴C]PF-07220060. 	
 The ratio of dose-normalized plasma AUC_{inf} of oral PF-07220060 (LCMS) and IV [¹⁴C]PF-07220060 (HPLC-AMS) [Cohort 2 only].

 To determine the fraction of PF-07220060 dose absorbed (F_a) from a single oral dose of [¹⁴C]PF-07220060 under fasted conditions. 	
 F_a calculated from the ratio of total recovered radioactivity [¹⁴C] in urine following single dose administration of [¹⁴C]PF-07220060 orally in Cohort 1 and via IV infusion in Cohort 2 (quantification by AMS).

 To determine the safety and tolerability of PF-07220060, administered as a single oral dose of [¹⁴C]PF-07220060 or a single oral dose of PF-07220060 followed by administration of a single IV dose of [¹⁴C]PF-07220060. 	
 AE monitoring, physical examination, clinical laboratory measurements, vital signs and 12-lead ECGs.
Tertiary/Exploratory:	Tertiary/Exploratory:

 To characterize the metabolic profile and identify the circulating and excreted metabolites of PF-07220060 following administration of a single oral dose of PF-07220060 followed by administration of a single IV dose of [¹⁴C]PF-07220060 (as needed). 	
 Contingent metabolic profiling/metabolite identification and determination of relative abundance of [¹⁴C]PF-07220060 and the metabolites of [¹⁴C]PF-07220060 in plasma, urine and feces, if possible (Cohort 2).

 To determine the plasma PK parameters of a single oral dose of PF-07220060 following administration as a single oral dose of [¹⁴C]PF-07220060 or a single oral dose of PF-07220060 followed by administration of a single IV microdose of [¹⁴C]PF-07220060. 	
 Plasma PK parameters of PF-07220060 from LCMS analyses (Cohort 1 and Cohort 2): 
 AUC_{last}, C_{max}, T_{max}. If data permits: AUC_{inf}, t_{1/2}, V_z/F, CL/F.

Objectives	Endpoints

 To determine plasma PK parameters of [^{14}C]PF-07220060 following administration of a single IV microdose of [^{14}C]PF-07220060. 	
 Plasma PK parameters of [^{14}C]PF-07220060 from HPLC-AMS analyses (Cohort 2): 
 AUC_{last}, C_{max}, T_{max}. If data permits: AUC_{inf}, $t_{1/2}$, CL, V_{ss}.

 To determine the urine PK parameters of PF-07220060 following administration as a single oral dose of [^{14}C]PF-07220060 (if measured) 	
 Urine PK parameters of PF-07220060 from LCMS (Cohort 1): 
 CL_R, Ae, and $\text{Ae}\%$.

 To determine plasma PK parameters of total radioactivity following administration of a single oral dose of [^{14}C]PF-07220060. 	
 Plasma PK parameters of total radioactivity [^{14}C] from AMS analyses (Cohort 1): 
 AUC_{last}, C_{max}, T_{max} of total radioactivity. If data permit: AUC_{inf}, $t_{1/2}$.

 To determine plasma PK parameters of total radioactivity following a single oral dose of PF-07220060 followed by administration of a single IV dose of [^{14}C]PF-07220060 (as needed). 	
 Plasma PK parameters of total radioactivity [^{14}C] from AMS analyses (Cohort 2): 
 AUC_{last}, C_{max}, T_{max} of total radioactivity. If data permit: AUC_{inf}, $t_{1/2}$.

 To explore the impact of pharmacogenomics on absorption, distribution, metabolism and excretion of [^{14}C]-PF-07220060 and the absolute bioavailability and fraction absorbed of PF-07220060. 	
 Allelic variants of drug metabolizing enzymes and transporters

 To evaluate the sensory and taste attributes of the PF-07220060 oral suspension in healthy participants under fasted conditions. 	
 Taste Assessment Survey Scoring Metrics: mouthfeel, bitterness, sweetness, sourness, saltiness, tongue/mouth burn, throat burn, and overall liking.

2.3. Study Design

This study will be a Phase 1, randomized, open-label, parallel-group, single-dose study of PF-07220060 to characterize the metabolic profile and routes of excretion for oral [^{14}C]PF-07220060 and to evaluate the absolute oral bioavailability (F) of PF-07220060 and fraction absorbed (F_a) of [^{14}C]PF-07220060, in reference to IV microtracer [^{14}C]PF-07220060 in fasted healthy male participants.

Approximately 6 healthy adult male participants will be enrolled in each of the 2 cohorts. Participants in Cohorts 1 and 2 will receive treatment regimen A and B, respectively. If there are participants who withdraw or discontinue treatment and are considered to be non-evaluable with respect to the primary and secondary PK objective(s), additional participants can be enrolled at the discretion of the investigator upon consultation with the sponsor.

3. ENDPOINTS AND BASELINE VARIABLES: DEFINITIONS AND CONVENTIONS

3.1. Primary Endpoints

Blood, urine, feces, and vomitus (if any) samples will be collected according to the schedule of activities (SoA) given in the protocol to analyze the following primary endpoints.

3.1.1. Mass Balance

Total Radioactivity in urine will be reported for **Cohort 1 and 2** separately, as the percentage of the administered radioactivity excreted at each time interval and as the cumulative total percent of dose excreted in urine over time.

Total Radioactivity in feces will be reported for **Cohort 1** (and if applicable for **Cohort 2**), as the percentage of the administered radioactivity excreted at each time interval and as the cumulative total percent of dose excreted in feces over time.

Total Radioactivity in vomitus (if any) will be reported for **Cohort 1 only**, as the percentage of the administered radioactivity excreted at each time interval and the total percent of dose recovered in vomitus.

Percent recovery of total radioactivity in urine, feces and vomitus for **Cohort 1 only**, will be determined based on total administered dose in **Cohort 1**. Residual radioactivity in the oral dosing container will be required to be assessed in **Cohort 1** and documented in the study CRF.

3.1.2. Metabolic Profiling and Metabolite Identification

Plasma, urine and fecal samples collected in Cohort 1 will be analyzed for metabolites of [¹⁴C]PF-07220060. Major metabolites of PF-07220060 in plasma, urine and feces may be identified if possible. Contributions of parent and each major metabolite to total radioactivity recovered in urine and feces and to circulating radioactivity in plasma will be quantified if possible.

3.2. Secondary Endpoints

3.2.1. Absolute Oral Bioavailability

Absolute oral bioavailability (F) will be estimated as the ratio of geometric mean of dose-normalized AUC_{inf} for oral unlabeled and IV labeled PF-07220060 (from Cohort 2 only) as per the following equation:

$$F = \frac{[PF-07220060_AUC_{po}/[^{14}C]-PF-07220060_AUC_{iv}] * [^{14}C]-PF-07220060_Dose_{iv}}{PF-07220060_Dose_{po}}$$

3.2.2. Fraction of PF-07220060 Dose Absorbed (F_a)

Fraction of dose absorbed (F_a) will be estimated as the ratio of total radioactivity (dose normalized) excreted into the urine (from time 0 to the time of last measurable concentration) following oral and IV administration of [¹⁴C]PF-07220060 microtracer doses in Cohort 1 and 2, respectively:

$$F_a = [\%^{14}C_Urine_PO / \%^{14}C_Urine_IV]$$

3.2.3. Safety Data

The following data will be considered in standard safety summaries (see protocol for collection days, baseline assessment, and list of parameters):

- Adverse events (AE)
- Laboratory data
- Vital signs data
- ECG results

3.2.3.1. Adverse Events

Any adverse events occurring following start of treatment will be considered as treatment emergent adverse event (TEAE). Events that occur during follow-up within the lag time of up to 35 days after the study drug dose will be counted as treatment emergent and attributed to the treatment taken. The time period for collecting AEs (“active collection period”) for each participant begins from the time the participant provides informed consent.

3.2.3.2. Laboratory Data

Safety laboratory tests will be performed as described in the protocol.

The baseline measurement is the predose measurement on Day -1. Changes from baseline will be defined as the change between the postdose and baseline measurements.

3.2.3.3. Vital Signs

Supine blood pressure (BP) and pulse rate (PR) will be measured at times specified in the SoA given in the protocol.

The baseline measurement is the predose measurement on Day 1. Changes from baseline will be defined as the change between the postdose and baseline measurements.

3.2.3.4. Electrocardiograms

QT interval, QTcF, PR, QRS and heart rate (HR) will be recorded at each assessment time indicated in the SoA given in the protocol. If not supplied, QTcF will be derived using Fridericia’s heart rate correction formula:

$$QTcF = QT / (RR)^{(1/3)} \text{ where } RR = 60/HR \text{ (if not provided)}$$

The baseline value is the predose ECG measurement on Day 1. Changes from baseline will be defined as the change between the postdose and baseline measurements.

3.3. Other Safety Endpoint(s)

None.

3.4. Exploratory Endpoints

3.4.1. Contingent Metabolic Profiling and Metabolic Identification

Plasma, urine and fecal samples collected in Cohort 2 will be analyzed for metabolites of [¹⁴C]PF-07220060. Major metabolites of PF-07220060 in plasma, urine and feces may be identified if possible. Contributions of parent and each major metabolite to total radioactivity

recovered in urine and feces and to circulating radioactivity in plasma will be quantified if possible. Results of the metabolic profiling analysis will be detailed in a separate report and will be summarized within the CSR.

3.4.2. Plasma PK Parameters of PF-07220060

Plasma PK parameters for PF-07220060 will be computed based on LCMS analysis of plasma samples.

The plasma PK parameters will be derived (as data permits) from the concentration-time data using standard noncompartmental methods as outlined in [Table 2](#). Actual PK sampling times will be used in the derivation of PK parameters. In the case that actual PK sampling times are not available, nominal PK sampling time will be used in the derivation of PK parameters.

Table 2. Plasma PK Parameters Definitions

Parameter	Definition	Method of Determination
AUC_{last}^a	Area under the plasma concentration-time profile from time 0 to time of the last quantifiable concentration (C_{last})	Linear/Log trapezoidal rule
$AUC_{last}(dn)$	Dose normalized AUC_{last} in Cohort 2 only	$AUC_{last}/Dose$
AUC_{inf}^a	Area under the plasma concentration-time profile from time 0 extrapolated to infinite time	$AUC_{last} + (C_{last}^*/k_{el})$, where C_{last}^* is the predicted plasma concentration at the last quantifiable time point estimated from the log-linear regression analysis, where k_{el} is the terminal phase rate constant calculated by a linear regression of the log-linear concentration-time curve. Only those data points judged to describe the terminal log-linear decline will be used in the regression
$AUC_{inf}(dn)^a$	Dose normalized area under the plasma concentration-time profile from time 0 extrapolated to infinite time, in Cohort 2 only	$AUC_{inf}/Dose$
C_{max}	Maximum plasma concentration	Observed directly from data
$C_{max}(dn)$	Dose normalized maximum plasma concentration, in Cohort 2 only	$C_{max}/Dose$
T_{max}	Time for C_{max}	Observed directly from data as time of first occurrence
$t_{1/2}^a$	Terminal elimination half-life	$\text{Log}_e(2)/k_{el}$
CL^a (IV)	CL: systemic clearance	$Dose/AUC_{inf}$
V_{ss}^a (IV)	V_{ss} : Steady state volume of distribution following IV infusion	$CL \times [MRT - (\text{infusion time}/2)]$ where MRT is the Mean Residence Time and is calculated as $AUMC_{inf}/AUC_{inf}$ $AUMC_{inf}$ is the area under the first moment curve from 0 time to infinity.
CL/F^a (oral)	Apparent clearance following oral administration	$Dose/AUC_{inf}$
V_z/F^a (oral)	Apparent volume of distribution following oral administration	$Dose / (AUC_{inf} * k_{el})$

Table 2. Plasma PK Parameters Definitions

Parameter	Definition	Method of Determination
F	Absolute oral bioavailability	$\frac{[AUC_{po}/^{14}CAUC_{iv}]*[^{14}C]\text{-PF-07220060_Doseiv}/PF\text{-07220060_Dosepo}}{}$ 
where, AUC_{po} is PF-07220060 area-under-the-plasma concentration curve following oral administration of unlabeled PF-07220060 PF-07220060_Dosepo: Oral dose of unlabeled PF-07220060 ¹⁴CAUC_{iv} is PF-07220060 area-under-the-plasma concentration curve following IV administration of [¹⁴C]PF-07220060 ¹⁴C-PF-07220060 Doseiv: IV dose of [¹⁴C]-PF-07220060 AUC_{inf} will be used unless data do not allow estimation of AUC_{inf}, in which case, AUC_{last} will be used

a. If data permits.

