#### 4.2. Scientific Rationale for Study Design

The purpose of the study is to assess the metabolism and excretion of [C]PF-07220060 following oral administration under fasted state conditions in healthy male participants. This information will enable assessment of primary and secondary clearance mechanisms of PF-07220060 as well as identify disproportionate metabolites that should be qualified to adhere to the ICH (M3) R2 guidance. In addition, this study will estimate the the fraction absorbed and bioavailability of oral PF-07220060 administered under fasted conditions in reference to an IV dose of [C]PF-07220060 and- will also assess plasma and urine PK parameters of PF-07220060 following both oral and IV administration of [C]PF-07220060. This characterization of absorption and oral bioavailability will enable the nomination of appropriate BCS designation for PF-07220060.

The study is being designed as a parallel-cohort study including 2 independent cohorts without crossover. Cohort 2 will be enrolled approximately 15 days after Cohort 1 enrollment. Cohorts 1 and 2 are enrolled sequentially using a single dose lifetime experimentation (one single PF-07220060 dose, no crossover) [REDACTED]  
[REDACTED]

Only males will be included in this study given the desire to enroll a homogeneous population due to the small sample size of this study. Dosing of PF-07220060 is planned to occur in the fasted state, which is consistent with the administration condition in the dose finding and dose optimization parts of Phase 1 study C4391001 in patients with cancer.

Due to lack of data on the elimination half lives of PF-07220060 metabolites, the minimum duration of confinement of [REDACTED] days was set as the timeframe when circulating PF-07220060 is expected to reach BLQ levels as determined based on the plasma half-life estimate from population PK modeling. An additional [REDACTED] days of permitted extended stay is to allow for excretion of any unknown metabolites with longer half-lives.

The duration of confinement and collection of blood, urine, and fecal samples for the participants in Cohort 2 will be matched with as the longest one from Cohort 1 in order to best estimate the  $F_a$  of PF-07220060.

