In this study, a “microtracer” approach will be used where the [ $^{14}\text{C}$ ] dose is much lower than traditional ADME studies. With this approach, [ $^{14}\text{C}$ ] will be quantified using an AMS detection technique. This technology allows ADME studies to be conducted without WBA data, as concentrations of [ $^{14}\text{C}$ ] and resulting exposures are so minute that dosimetry calculations are not needed.

**Cohort 1** of the study is designed to evaluate the metabolic fate and mass balance of PF-07220060 following the intended clinical route of administration (oral) of [ $^{14}\text{C}$ ]PF-07220060. In order to assess the metabolic fate of [ $^{14}\text{C}$ ]PF-07220060, metabolites of [ $^{14}\text{C}$ ]PF-07220060 circulating in plasma and eliminated in urine and feces following oral administration will be determined using AMS. Additionally, mass balance will be determined by recovery of total radioactivity excreted in urine and feces. Lastly, the plasma PK of PF-07220060 (via LCMS) will be compared to plasma PK of total radioactivity (via AMS) for determination of relative abundance as an additional way to quantify circulating metabolites.

**Cohort 2** of the study is designed to evaluate the  $F$  and estimate  $F_a$  of the oral PF-07220060 dose. A microtracer microdose (CCl4 nCi, CCl4 μg) of [ $^{14}\text{C}$ ]PF-07220060 will be administered via a 30 minutes IV infusion at the approximate  $T_{\max}$  following an oral unlabeled 100mg- dose of PF-07220060 and labeled [ $^{14}\text{C}$ ]PF-07220060 in plasma will be assessed via AMS following chromatographic separation (HPLC-AMS).  $F$  will be calculated as the ratio of dose-normalized plasma  $\text{AUC}_{\text{inf}}$  following orally administered PF-07220060 (ie, unlabeled PF-07220060 assessed by LCMS) to dose-normalized- plasma  $\text{AUC}_{\text{inf}}$  following intravenously administered [ $^{14}\text{C}$ ]PF-07220060 (ie [ $^{14}\text{C}$ ]PF-07220060 assessed by HPLC-AMS).

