**Table 3. Plasma PK Parameters Definitions**

Parameter	Definition	Method of Determination
$AUC_{last}^a$	Area under the plasma concentration-time profile from time 0 to time of the last quantifiable concentration ( $C_{last}$ )	Linear/Log trapezoidal rule
$AUC_{last}(dn)$	Dose normalized $AUC_{last}$ in Cohort 2 only	$AUC_{last}/Dose$
$AUC_{inf}^a$	Area under the plasma concentration-time profile from time 0 extrapolated to infinite time	$AUC_{last} + (C_{last}^*/k_{el})$ , where $C_{last}^*$ is the predicted plasma concentration at the last quantifiable time point estimated from the log-linear regression analysis, where $k_{el}$ is the terminal phase rate constant calculated by a linear regression of the log-linear concentration-time curve. Only those data points judged to describe the terminal log-linear decline will be used in the regression
$AUC_{inf}(dn)^a$	Dose normalized area under the plasma concentration-time profile from time 0 extrapolated to infinite time, in Cohort 2 only	$AUC_{inf}/Dose$
$C_{max}$	Maximum plasma concentration	Observed directly from data
$C_{max}(dn)$	Dose normalized maximum plasma concentration, in Cohort 2 only	$C_{max}/Dose$
$T_{max}$	Time for $C_{max}$	Observed directly from data as time of first occurrence
$t_{1/2}^a$	Terminal elimination half-life	$\log_e(2)/k_{el}$
$CL^a$ (IV)	CL: systemic clearance	$Dose/AUC_{inf}$
$V_{ss}^a$ (IV)	$V_{ss}$ : Steady state volume of distribution following IV infusion	$CL \times [MRT - (infusion\ time/2)]$ where MRT is the Mean Residence Time and is calculated as $AUMC_{inf}/AUC_{inf}$ $AUMC_{inf}$ is the area under the first moment curve from 0 time to infinity.
$CL/F^a$ (oral)	Apparent clearance following oral administration	$Dose/AUC_{inf}$
$Vz/F^a$ (oral)	Apparent volume of distribution following oral administration	$Dose / (AUC_{inf} * k_{el})$
F	Absolute oral bioavailability	$[AUC_{po}/^{14}CAUC_{iv}] * [^{14}C]-PF-07220060\_Dose_{iv}/PF-07220060\_Dose_{po}]$ where, $AUC_{po}$ is PF-07220060 area-under-the-plasma concentration curve following oral administration of unlabelled PF-07220060 PF-07220060_Dose po : Oral dose of unlabelled PF-07220060 $^{14}CAUC_{iv}$ is PF-07220060 area-under-the-plasma concentration curve following IV administration of $[^{14}C]$ -PF-07220060 $[^{14}C]$ -PF-07220060 Dose iv : IV dose of $[^{14}C]$ -PF-07220060 $AUC_{inf}$ will be used unless data do not allow estimation of $AUC_{inf}$ , in which case, $AUC_{last}$ will be used

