5.3. Methods to Manage Missing Data

5.3.1. Pharmacokinetic Data

Methods to handle missing PK data are described below.

Concentrations Below the Limit of Quantification:

In all data presentations (except listings), concentrations below the limit of quantification (BLQ) will be set to zero. (In listings BLQ values will be reported as “<LLQ”, where LLQ will be replaced with the value for the lower limit of quantification.).

Deviations, Missing Concentrations and Anomalous Values:

In summary tables and plots of median profiles, statistics will be calculated having set concentrations to missing if one of the following cases is true:

1. A concentration has been collected as ND (ie, not done) or NS (ie, no sample).
2. A deviation in sampling time is of sufficient concern or a concentration has been flagged as anomalous by the pharmacokineticist.

Note that summary statistics will not be presented at a particular time point if more than 50% of the data are missing.

An anomalous concentration value is one that, after verification of bioanalytical validity, is grossly inconsistent with other concentration data from the same individual or from other participants. For example, a BLQ concentration that is between quantifiable values from the same dose is considered as anomalous. Anomalous concentration values may be excluded from PK analysis at the discretion of the PK analyst or pharmacokineticist.

PK Parameters:

Actual PK sampling times will be used in the derivation of PK parameters. If a PK parameter cannot be derived from a participant's concentration data, the parameter will be coded as NC (ie, not calculated). (Note that NC values will not be generated beyond the day that a participant discontinues). In summary tables, statistics will be calculated by setting NC values to missing; and statistics will be presented for a particular treatment with ≥ 3 evaluable measurements. PK parameter analyses will not be performed for a particular parameter if more than 50% of the data are NC.

If an individual participant has a known biased estimate of a PK parameter (due for example to an unexpected event such as vomiting before all the compound is adequately absorbed from the gastrointestinal tract), this will be footnoted in summary tables and will not be included in the calculation of summary statistics or statistical analyses.

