6.2. Secondary Endpoints

6.2.1. Absolute Oral Bioavailability

Natural log transformed $AUC_{inf}(dn)$ (if data permit) and $AUC_{last}(dn)$ from Cohort 2 will be analyzed using a mixed effect model with treatment as a fixed effect and participant variable as a random effect. Estimates of the adjusted (least squares) mean differences (Test/Reference) and the corresponding 90% confidence interval in log-scale will be obtained from the model. The adjusted mean differences and 90% confidence intervals for the differences will be exponentiated to provide estimates of the ratio of adjusted geometric mean (Test/Reference) and 90% confidence interval for the ratio. IV [^{14}C]PF-07220060 will be considered the Reference formulation and unlabeled oral PF-07220060 will be considered the Test formulation.

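### The AUClast ratio used as the fallback and supportive estimate of F sets no common end time for the oral LCMS and IV HPLC-AMS profiles, so it can shift with relative assay sensitivity

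*SAP*

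**What the plan says.** F is a secondary endpoint, estimated in Cohort 2 only as the oral-to-IV ratio of dose-normalized AUCinf (protocol 3 and 9.3.2.1; SAP 3.2.1). The two areas come from different doses and assays (protocol 4.2). The oral area follows 100 mg ("unlabeled PF-07220060 assessed by LCMS"). The IV area follows a radiolabeled microdose ("PF-07220060 assessed by HPLC-AMS").

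The F row of SAP Table 2, repeated in protocol Table 3, says that AUCinf "will be used unless data do not allow estimation of" AUCinf; AUClast then takes its place. SAP Table 2 defines AUClast as "Area under the plasma concentration-time profile from time 0 to time of the last quantifiable concentration", and protocol Table 3 also runs it "to time of the last quantifiable concentration". Neither document sets an end time common to the two routes.

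For the model, SAP 6.2.1 (and protocol 9.3.2.1) states that log AUCinf(dn), if data permit, and log AUClast(dn) "from Cohort 2 will be analyzed using a mixed effect model with treatment as a fixed effect and participant variable as a random effect". The AUClast(dn) run carries no such condition. SAP 5.3.1 drops the analysis of a parameter when more than half its values are not calculated. SAP 6.4 lists the terminal-fit diagnostics (r², percent extrapolated, points used) but attaches no acceptance limit to them.

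Protocol 4.1 calls the drug highly permeable if F or Fa exceeds 0.9, and lets the larger value stand for fraction absorbed when F exceeds Fa.

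**The concern.** An AUC ratio measures bioavailability only if numerator and denominator capture the same share of their total areas. AUCinf meets this by extrapolation. AUClast does not: its end point depends on how far each assay can follow its own dose. Protocol 4.2 sets the minimum stay at the time when "circulating PF-07220060 is expected to reach BLQ levels", so the last quantifiable time is likely to be set by the assay limit and not by the last scheduled sample.

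The AUClast ratio matters in three situations:

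- It is planned with a 90% confidence interval whether or not AUCinf succeeds.
- It becomes the only model-based F if more than half of the AUCinf values are not calculated. With 6 participants that is 4 failures if counted within a route; the SAP does not say how to count.
- Under the Table 2 rule it replaces AUCinf in an individual F value.

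An upward error could carry F past 0.9. A lower Fa would not offset it, because either value can trigger the permeability conclusion and the larger one is used.

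**Working it through.** **Stated figure.** The plan gives no numerical F, power or bias figure for this point, so there is nothing to reproduce.

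**Identity.** Let p(oral) and p(IV) be the fractions of each total area captured by its own last quantifiable time. Then

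AUClast(dn) ratio = F × p(oral) / p(IV).

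The identity needs no kinetic model. For example, 99% captured orally and 90% IV multiplies F by 0.99/0.90 = 1.10; 80% orally and 99% IV multiplies it by 0.80/0.99 = 0.81.

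**Simple illustration.** Assumptions, not in the documents: mono-exponential decline, half-life h of 10, 15 or 20 h, and last quantifiable times of 72 h for one route and 36 h for the other. The captured fraction is p(t) = 1 − 2^(−t/h).

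| h (h) | p(72) | p(36) | Oral 72, IV 36 | Oral 36, IV 72 |
|---|---|---|---|---|
| 10 | 0.993 | 0.918 | 1.082 | 0.924 |
| 15 | 0.964 | 0.811 | 1.189 | 0.841 |
| 20 | 0.918 | 0.713 | 1.287 | 0.777 |

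The ratio is therefore +8% to +29% one way and -8% to -22% the other. In the first direction, a true F above 0.9/1.082 = 0.83, 0.9/1.189 = 0.76 or 0.9/1.287 = 0.70 would show as more than 0.9.

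**Check on the trial's schedule.** Inputs from protocol Table 2: the Cohort 2 nominal times and the 30-minute infusion. Assumed: a noiseless one-compartment model, half-lives of 8, 15 and 24 h, absorption rate 0.5 or 1.0 per h, true F of 0.4, 0.6 or 0.8, and daily samples after 96 h. Quantification limits are expressed as a percentage of the dose-normalized IV Cmax. AUC is by the linear/log trapezoid.

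- Oral 1%, IV 1%: -4% to 0%.
- Oral 1%, IV 10%: +9% to +15%. A true F of 0.8 is reported as about 0.90 to 0.92; the lowest case, 0.896, stays just under 0.9.
- Oral 10%, IV 1%: -36% to -12%.

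**Mixed AUC types.** Oral AUCinf over IV AUClast, with 18.9% of the IV area beyond the last sample (h = 15 h, 36 h), multiplies F by 1/0.811 = 1.23. The example code in SAP Appendix 2 models one variable at a time, so each run uses the same AUC type for both routes. This case can arise only in an individual F value derived under Table 2.

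**Common end time.** Cutting both areas at the shorter of the two last quantifiable times, counted from each route's own dose, brings the bias to between about -8% and 0% where the IV assay is limiting, mostly within -4%. The residual is downward because oral input lags IV input. The worst case across the scenarios is roughly -18%, where the oral profile ends at 8 h.

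**The case against.** The strongest reply is that the fallback is unlikely to be used. AUCinf is the stated endpoint. Sampling runs to between 96 and 312 h after the oral dose (94 to 310 h after the start of infusion), and the minimum stay is tied to the drug falling below quantification. In the illustration itself, an IV profile quantifiable to 36 h would have some ten post-dose samples by 34 h, enough to fit a terminal slope, and the SAP has no extrapolation limit that would reject the result. This stands: the 8% to 29% figures describe the AUClast(dn) ratio, not a fallback that those scenarios would trigger.

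It is also true that no quantification limit or last quantifiable time is given, and that protocol 4.1 chose AMS for its sensitivity to the microtracer dose. A reader might infer that the end times do differ and that F is biased upward. The documents show only that they are free to differ, in either direction.

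A reader might also infer that the planned F could be overstated by 23% through pairing AUCinf with AUClast. The mixed model does not allow this, and SAP Table 4 does not list F among the parameters to be summarized.

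Finally, both ratios are reported and the terminal-fit diagnostics are listed, so a discrepancy would be visible. That helps while both ratios exist. It does not help when AUClast(dn) is the only one left.

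**Conclusion.** The point holds in a limited form. The plan specifies an AUClast ratio as a routine second estimate of F and as the replacement if AUCinf fails, without a common end time, across routes that differ in dose and assay. That ratio combines F with relative assay sensitivity.

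The size and sign are unknown. They range from negligible (about 0 to -4%) if relative sensitivities match to some tens of percent if they do not; all these figures rest on assumed half-lives, kinetics and quantification limits. The documents do not support reading this as a demonstrated bias in the main AUCinf-based F. F is a secondary endpoint and no hypothesis is tested. The consequence to guard against is an AUClast-based F being read against 0.9. The change is worth making before analysis, so that the AUC type is not chosen after the ratios are known.

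**What to change.** Amend protocol Table 3 and 9.3.2.1, and SAP Table 2 and 6.2.1, as follows.

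1. Keep AUCinf(dn) as the main measure for F.
2. Where AUCinf does not support the analysis, base F for all Cohort 2 participants on one substitute, not participant by participant. The substitute is a dose-normalized AUC from each route's own dose time to the last time after dose at which both analytes are quantifiable in that participant. After 6 h the oral and IV nominal times, each counted from its own dose, do not coincide, so state the interpolation rule.
3. Model this common-time AUC in place of AUClast(dn) as the supportive ratio. AUClast may still be listed.
4. Require the same AUC type for both routes in every F value, including individual ones.
5. State when an AUCinf counts as not calculated, and whether the 50% rule in SAP 5.3.1 is counted per route or over both.

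The cost is one derived parameter and some wording, with no extra samples or visits. Some late concentrations from the more sensitive assay go unused in this ratio. The small downward bias from the oral input lag remains (mostly within -4%, larger if the oral profile ends very early) and should be stated when the ratio is reported.
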